Study Protocol with SAP

Title:

Evaluating the Safety and Efficacy of Fractionated Carbon Dioxide Therapy in Postoperative Lower Extremity Wound Healing

NCT number:

NCT03644849

Document date:

April 7, 2021

Upload date:

November 7, 2021

Purpose: This study will evaluate the efficacy and safety of laser therapy on postoperative lower extremity wound healing over 12 weeks. We will include adult patients who have undergone Mohs Micrographic Surgery on their lower extremities. Patients with poor immune systems, current pregnancies, uncontrolled diabetes, lower extremity venous or arterial disease will not be included in this study. After surgery patients will be randomized into two groups. One group will receive a single laser treatment immediately after their surgery on their wound while the other will not. The group not receiving laser therapy will undergo a sham laser therapy treatment. Immediately after therapy and 4, 8, and 12 weeks postoperative patients will have a follow up visit. During these visits patients wound size will be recorded, whether the wound has healed, a photograph will be taken, and the wound temperature will be measured. Patient will be given a diary to record any adverse events related to the wound and will fill out a quality of life survey.

Objectives (specific aims and hypotheses): We hypothesize that the AFL carbon dioxide ablative laser is a safe and efficacious treatment for lower extremity wounds that result from skin cancer surgery. We plan to test this hypothesis in 2 specific aims:

Aim 1. We will establish the safety and tolerability of the carbon dioxide AFL for postoperative lower extremity wounds. Patients with postoperative lower extremity wounds will be randomized to sham laser versus laser therapy. At designated time points 0-12 weeks after sham or laser treatment, patients will return to clinic for assessment of safety endpoints, including the incidence of wound infection and tolerability using a patient diary and health-related quality of life measured using a standardized generic questionnaire such as EQ. A sample size of 48 is appropriate.

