Patients will be seen at 4 separate visits to monitor safety and efficacy endpoints (4, 8 and 12 weeks post-operatively). The patient's initial visit will include preoperative screening for eligibility, informed consent procedure, and recording of past medical history and physical exam. Once the patient is deemed eligible, enrolled, and signed informed consent, they will be randomized to either carbon dioxide AFL therapy or sham laser therapy. After the patient undergoes Mohs surgery with the resultant ulcer (the defect that typically forms after Mohs), the patient will undergo either carbon dioxide laser versus sham laser therapy. We will determine presence or absence of complete healing, wound temperature, a digital photograph, quality of life, and adverse events at each visit. Healing will be determined by one of the licensed research team members and will be defined by complete epithelialization in the absence of scab/eschar.

Wound temperature will be recorded by noninvasive infrared thermographic camera. A digital photograph will be taken with a camera that has an attachment ensuring the same distance and angle at every visit. Quality of life will be determined by ED-5Q questionnaire. Adverse events will be recorded by eliciting an oral history and review of the patient's diary. Adverse events will be recorded as presence of absence of specific outcomes. Outcomes that patients will be directly questioned about include: crusting (scaly or thickened scar), swelling, burning sensation, xerosis at treatment site, pruritus at treatment site, infection, bleeding, hypertrophic or keloid scarring, burns, or color changes at treatment site. These data points will be collected at every visit, and adjudicated by a member of the research team blinded to the treatment group. Placebo treatment will consist of directing the laser system at the floor instead of the patient's wound site. The patients will be wearing safety glasses and will have their wound site still anesthetized from the operation therefore unaware if they are receiving the therapy. This group will serve as the control group to the treatment arm in the study.

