Statistical / Data analysis: We estimate that 48 participants will be required to show a significant difference in time to 100% epithelialization between treatment and control during the 12 week study. A power analysis conducted in R(1) using the powerSurvEpi package(2) with alpha = 0.10 and beta = 0.20 suggested 24 participants per group or 48 total were required. We will employ various statistical techniques in addressing our study aims. For our first aim, efficacy: time to epithelialization will be modeled in a Cox regression as a function of covariates and treatment status. Temperature will be similarly modeled, but for these outcomes we will examine effects across time via a linear mixed model. For our second aim, safety: we intend to model incidence of infection as well as quality of life again across time using linear mixed models but this time based on non-inferiority comparisons. To address any attrition, we will employ per-protocol analysis. In the interest of safety, we plan to perform interim analyses at one month and discontinue the study if warranted.

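### Wound infection is named as an incidence but analysed as repeated visit scores with no stated contrast or margin, so a visit-averaged non-inferiority comparison could understate a real excess, by up to four-fold in the worst case

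*Combined protocol and SAP*

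**What the plan says.** Under Objectives, Aim 1 provides for "assessment of safety endpoints, including the incidence of wound infection". It gives no rule for turning infection into a per-patient outcome.

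Under Patient Visits and Data Collection, infection is one of the listed adverse events: "Adverse events will be recorded as presence of absence of specific outcomes". The same section adds: "These data points will be collected at every visit". The source is oral history plus the patient's diary. The text does not say whether a visit score means new since the last visit, present on the day, or ever present.

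The Purpose section sets the schedule: "Immediately after therapy and 4, 8, and 12 weeks postoperative patients will have a follow up visit". The data-collection section words it differently: "Patients will be seen at 4 separate visits to monitor safety and efficacy endpoints (4, 8 and 12 weeks post-operatively". That is a count of four with three times listed, and the fourth is presumably the day of treatment.

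The Statistical / Data analysis section then says: "we intend to model incidence of infection as well as quality of life again across time using linear mixed models", to be judged by non-inferiority. It calls safety the second aim, whereas Objectives calls it Aim 1. It does not name the treatment contrast (visit-averaged, by visit, or slope), say whether day 0 enters the infection model, or give a margin or its scale. The sample size of 24 per group is derived for time to epithelialization only.

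**The concern.** The incidence of infection over follow-up is the proportion of patients who become infected. A present/absent score repeated over visits and averaged by a mixed model gives something else: the mean proportion of visits at which infection is present. An infection that resolves between visits counts once, and one that persists counts several times. Visits at which nobody is infected pull both arms toward zero.

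The direction matters because the comparison is for non-inferiority. A difference that is compressed toward zero, and then compared with a margin chosen for the proportion of patients infected, makes the laser look safer than it is. The potential error is false reassurance about a safety endpoint.

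**Working it through.** **Plan's own figure.** There is none to reproduce. The plan gives no expected infection rate, margin or power for this comparison. The 24 per group (alpha 0.10, beta 0.20) belongs to the healing endpoint.

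**Inputs from the documents.** 24 patients per arm; binary scoring at each visit; four visits if the one immediately after therapy counts, three if not.

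**Assumptions (not in the documents).** 12-week infection risk of 5% on sham and 20% on laser; margins of 5, 10 and 15 points; one-sided 5% upper confidence bound (z = 1.645); complete data; no infection scored at day 0.

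**Step 1: dilution.** With complete data, the treatment main effect of a random-intercept model is the difference between arms in patient means over visits. If every infected patient is positive at *v* of *K* visits:

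visit-averaged difference = (*v*/*K*) × difference in proportion infected.

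The assumed difference in proportion infected is 20 − 5 = 15 points.

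| Positive visits / visits in model | Visit-averaged difference | Understatement |
|---|---|---|
| 1 of 4 (day 0 included) | 15 × 1/4 = 3.75 points | 4.0-fold |
| 1 of 3 (day 0 excluded) | 15 × 1/3 = 5.0 points | 3.0-fold |
| 2 of 4 | 15 × 2/4 = 7.5 points | 2.0-fold |
| 3 of 4 | 15 × 3/4 = 11.25 points | 1.33-fold |

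A mixed model fitted to simulated data agreed. For a difference of 0.142 in the proportion infected, the main effect was 0.0355 with day 0 (0.142/4) and 0.0473 without it (0.142/3). The fit gave convergence warnings, but with balanced complete data these ratios follow algebraically. With treatment-by-visit terms and about 80% of infections scored at week 4, the week-4 contrast was 0.1225, and 0.142/0.1225 ≈ 1.2-fold.

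**Step 2: effect on the non-inferiority decision (illustrative).** Share of simulated trials declaring non-inferiority at 5% v 20%, with the same numerical margin applied to each quantity and standard errors from patient-level values:

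| Quantity compared with the margin | 5 points | 10 points | 15 points |
|---|---|---|---|
| Proportion of patients infected | 1% | 3% | 7% |
| Four-visit average, one positive visit | 17% | 85% | 99.7% |
| Three-visit average, one positive visit | 7% | 53% | 93% |
| Four-visit average, two positive visits | 3% | 17% | 53% |

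At 10 points the week-4 contrast passes in about 6% of trials.

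**Step 3: does rescaling the margin remove the problem?** If every infection is positive at exactly one visit, the estimate and its standard error shrink by the same factor. With the 10-point margin rescaled to 10/4 = 2.5 points, the pass rate returns to about 3%, the per-patient figure. That equivalence needs equal durations in both arms. Suppose 20% of laser patients are positive at one of four visits and 10% of sham patients at two of four:

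- laser: 20% × 1/4 = 5% per visit
- sham: 10% × 2/4 = 5% per visit
- visit-averaged difference: 0, although the proportion infected has doubled.

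No choice of margin on the visit scale recovers the incidence difference in that case.

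**The case against.** The strongest reply is that the plan is under-specified, not demonstrably biased. The four-fold figure needs four things at once: a visit-averaged contrast, one positive visit per infected patient, day 0 in the model, and a margin set on the cumulative scale. The documents state none of them. Modelling across time is equally compatible with treatment-by-visit contrasts, where the loss may be only about 1.2-fold. Since adverse events come from oral history and diary, a score could be carried forward as ever infected, so that most infections would be positive at several visits. The schedule in the data-collection section lists only weeks 4, 8 and 12. Averaging alone also does not favour non-inferiority if the margin is on the same scale and durations are alike.

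All of this stands as a limit on the size. A reader might infer that the planned analysis will dilute an infection excess four-fold, or that 85% v 3% describes this trial. The documents support neither: those figures come from one corner of assumed risks, durations, contrast and margin. Nor do the documents say that infection is impossible on day 0; that is an assumption here.

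The objection does not remove the point. The open choices are ones the plan has to make, and nothing in the text rules out the unfavourable combination. Rescaling the margin fails when infection durations differ between arms. A repeated visit score, however contrasted, is not defined in the plan as the incidence that Aim 1 names.

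**Conclusion.** The concern holds in conditional form. The named endpoint is an incidence, while the recorded and modelled variable is presence at each visit, and the plan supplies no per-patient definition, contrast or margin to connect them. If a visit-averaged difference is judged against a cumulative-incidence margin, an excess could be understated by 4-fold at most with four visits and 3-fold at most with three. The factor is 2-fold when infections are scored at two of four visits, and about 1.2-fold for a week-4 contrast with most infections scored then. The factors rest on complete data, equal infection duration in both arms and no infection scored at day 0. The pass rates rest additionally on assumed risks and margins and are illustrative only. In the equal-duration cases with a fixed numerical margin, the error runs toward declaring the laser safe. With unequal durations the visit average can miss a doubled risk altogether.

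**What to change.** In the Statistical / Data analysis section:

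- Define the infection endpoint as one value per patient: any wound infection after treatment through week 12 (yes/no), from the visit assessments, oral history and diary already collected.
- Compare the arms as a difference in 12-week risk, with a confidence interval suited to sparse binary data.
- State the non-inferiority margin on that same scale, with its justification and the confidence level. A per-patient endpoint without a margin still cannot support a non-inferiority claim.
- Report visit-level presence descriptively, and say what a visit score means (new, current or ever).
- Reconcile the four-visit count with the three listed times, and the numbering of the safety aim.

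The change is to wording only and needs no new data. The cost is a wide interval. Under the assumed 5% v 20%, the standard error is √(0.05×0.95/24 + 0.20×0.80/24) ≈ 0.093, so a one-sided 5% bound lies about 1.645 × 9.3 ≈ 15 points above the estimate. Even with 5% in both arms it is √(2×0.05×0.95/24) ≈ 0.063, or about 10 points above. These are large-sample approximations, used only to show scale. Non-inferiority will be harder to show with 24 per arm, which reflects how little 48 patients can say about infection risk.

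### Nine of the ten collected adverse events, and the diary tolerability endpoint of Aim 1, have no planned between-arm summary, and the only analysis set named is per-protocol

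*Combined protocol and SAP*

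**What the plan says.** The Objectives section gives the hypothesis ("We hypothesize that the AFL carbon dioxide ablative laser is a safe and efficacious treatment for lower extremity wounds") and sets Aim 1: "We will establish the safety and tolerability of the carbon dioxide AFL for postoperative lower extremity wounds". The endpoints follow as "assessment of safety endpoints, including the incidence of wound infection and tolerability using a patient diary and health-related quality of life", the last measured by a generic questionnaire.

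Patient Visits and Data Collection lists ten outcomes that patients are asked about directly. Five are crusting, swelling, a burning feeling, dryness and itch. The other five are "infection, bleeding, hypertrophic or keloid scarring, burns, or color changes at treatment site". On format it says "Adverse events will be recorded as presence of absence of specific outcomes", and on timing and assessment "These data points will be collected at every visit, and adjudicated by a member of the research team blinded to the treatment group".

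Statistical / Data analysis is the whole analysis plan. Its safety sentence reads "we intend to model incidence of infection as well as quality of life again across time using linear mixed models". The type of comparison is given at the end of that sentence: "but this time based on non-inferiority comparisons". (That section calls safety the second aim; in Objectives it is Aim 1.) Attrition is to be handled by per-protocol analysis. No other analysis set is named, and the per-protocol set is not defined.

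There are two further safety provisions. Under Blinding, the unblinded treating clinician reports adverse events under the institution's IRB procedures. Under Statistical / Data analysis, an interim analysis at one month may lead to stopping the study; no endpoint or criterion is given for it.

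**The concern.** The protocol collects a detailed, blinded adverse event record and then specifies a comparison for only one item on it. What is done with the other nine is left to be settled after the data are seen: which events are shown, over what period, in which patients and with what measure of uncertainty. That is the choice an analysis plan should fix beforehand, above all when the trial hopes to call an ablative treatment of a fresh wound safe.

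The per-protocol rule adds a second problem. It is stated without exception, so it reaches the safety analyses. A patient who is treated, has a bad local reaction and stops attending could fall outside the set. Losses of that kind would be related to the outcome being measured and would lower the apparent event rate.

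**Working it through.** **Plan's own figure.** The only design figure is 24 per arm, 24 + 24 = 48 in total, sized for time to full epithelialization at alpha 0.10 and beta 0.20. No hazard ratio or healing probability is given, so it cannot be reproduced. This point does not depend on it; 24 per arm is used below only as a denominator.

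**Step 1: collected against analysed.**

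| Item | Collected | Between-arm analysis specified |
|---|---|---|
| Infection | every visit, blinded adjudication | yes, non-inferiority, linear mixed model |
| Quality of life | every visit | yes, non-inferiority, linear mixed model |
| Crusting, swelling, burning sensation, xerosis, pruritus | every visit, blinded adjudication | none |
| Bleeding, abnormal scarring, burns, colour change | every visit, blinded adjudication | none |
| Diary tolerability (Aim 1) | diary | none |

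Of the ten events, 10 − 1 = 9 have no specified comparison.

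**Step 2: do the other provisions fill the gap?** IRB reporting concerns individual events and does not compare arms. The one-month analysis has no stated endpoint and cannot cover events that appear between then and week 12. Neither compares the nine events by arm over the whole follow-up.

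**Step 3: what a by-arm table could show.** All event counts here are assumptions, with full follow-up of 24 per arm.

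- No events in an arm: exact two-sided 95% upper limit = 1 − 0.025^(1/24) = 14.2%.
- 5 of 24 (20.8%): exact (Clopper-Pearson) 95% interval 7.1% to 42.2%.
- Two-sided Fisher test for y v 0 events: p = 2 × C(24,y)/C(48,y). This gives 0.489 for 2 v 0, 0.234 for 3 v 0, 0.109 for 4 v 0, 0.0496 for 5 v 0 and 0.022 for 6 v 0.
- Fisher power at two-sided 0.05: 75% for true rates of 25% v 0%, but 31% for 30% v 10%.
- Nine tests at 0.05, if independent, have a familywise error of 1 − 0.95^9 = 37%.

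So a large excess in one event would be visible and a moderate one usually would not reach significance. Estimates with intervals suit these data better than nine or ten tests.

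**Step 4: what the per-protocol set could do.** Suppose 5 of 24 laser patients have an event and k of those five are dropped. The observed rate becomes (5 − k)/(24 − k): 20.8% for k = 0, 4/23 = 17.4% for k = 1, 3/22 = 13.6% for k = 2, and 0/19 = 0% for k = 5. The documents give no basis for choosing k. The range shows the direction of the effect and how sensitive a small arm is.

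**The case against.** The strongest reply is that silence is not exclusion. Aim 1 introduces its endpoints with the word including, so its list is open. The events are recorded and adjudicated with care, and nothing says they will not be tabulated. This stands. A reader might infer that the plan has a rule that declares safety from infection and quality of life alone and so shuts the other events out. The documents contain no such rule: there is no non-inferiority margin, no threshold and no statement of what safe would require. The gap is in what is specified.

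Four further limits also stand.

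- A reader might say that tolerability gets no between-arm result at all. The Aim 1 sentence can be read as measuring tolerability by both diary and quality of life. On that reading only the diary part lacks a comparison.
- A reader might call burns, bleeding, scarring and colour change laser-specific. The documents do not attribute or rank the ten events, and both arms have fresh surgical wounds.
- A reader might infer that a clear excess would be ignored whatever happened. IRB reporting and the interim analysis could pick up a gross problem, although neither is a comparison to week 12.
- A count such as 5 v 0 for burn or scar combined is hypothetical and just at the threshold (p = 0.0496). Split item by item as 3 v 0 and 2 v 0, it gives p = 0.234 and p = 0.489. It does not show that a harm would be clearly worse on laser.

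None of this supplies the missing summary or limits the per-protocol rule to efficacy.

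**Conclusion.** The concern holds in a limited form. Nine of the ten adverse events, and the diary tolerability endpoint, have no specified between-arm comparison, and the only named analysis set is per-protocol. As written, the specified safety analyses could be favourable without reflecting those events, and treated patients who left after a harm could be omitted. That the laser could be called safe on this basis is an inference from the absence of any other specified comparison; the plan does not say it.

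The size is a matter of coverage, and no bias can be computed from the documents. The numerical illustrations rest on assumed event counts and 24 patients followed per arm. The change is worth making because it replaces the per-protocol rule with a sounder set for safety and gives Aim 1 a result on data already being collected.

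**What to change.** Add to Statistical / Data analysis:

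1. For each of the ten outcomes listed under Patient Visits and Data Collection, the number of patients with the event will be given by arm, at each visit and at any time from treatment to week 12, with exact 95% confidence intervals and a risk difference.
2. These summaries will include all treated patients, grouped by treatment actually received, and will not be restricted to the per-protocol set. Showing the number assessed at each visit will make attrition visible.
3. The Aim 1 safety and tolerability conclusion will be drawn from these summaries together with infection and quality of life.
4. The comparisons are estimates, not tests.

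The cost is one paragraph and one table, with no new data and no change in conduct. The drawback is about ten descriptive comparisons without multiplicity control and with wide intervals. An arm with no events should be reported with its upper limit (14.2% for 0 of 24), so that absence of events is not read as proof of safety.

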Aim 2. Determine the efficacy of the carbon dioxide AFL for healing postoperative lower extremity wounds. We plan to randomize n=48 patients with post-surgical lower extremity wounds to sham versus carbon dioxide fractional laser treatment. We will determine the time to complete ulcer healing over a 12 week course of follow up. Completion of these aims will likely improve care for hundreds of thousands of patients with lower extremity ulcers by extending the use of ablative fractional lasers to a new population of patients. Future studies will be needed to address the efficacy of ablative laser technology in ulcers of other etiologies, and have the potential to impact the lives of many patients.

Study Design: Our study is a prospective, double-blinded, randomized, placebo-controlled trial evaluating the efficacy of fractionated carbon dioxide therapy in postoperative lower extremity wound healing. This study, including analysis and submission for publication, will occur from September 2018 to November 2020. Eligibility criteria will include patients older than 18 years, those with a lower extremity wound as a result of Mohs Micrographic Surgery at Saint Louis University Dermatology Des Peres, and a postoperative wound greater than 5mm in diameter. Patients must be able to understand the informed consent, willing to come to the office for treatments and capable of following posttreatment instructions. Exclusion criteria will include pregnancy, immunosuppression, uncontrolled diabetes (defined as >7% A1c in the last 3 months), peripheral vascular disease, venous insufficiency, or no desire/unable to undergo laser therapy. After informed consent is obtained, a screening visit will be performed on their Mohs surgery day and patient eligibility will be determined. Then, patients will be randomized 1:1 to a treatment or control group via computer software. One arm will receive carbon dioxide AFL

immediately postoperatively on the wound base. The second arm, which will serve as control, will receive sham laser therapy. Both patients will be given identical postoperative wound care instructions, including vaseline applied to the wound, nonstick pad to overlay the wound, and paper tape to secure the dressing. Additionally, patients will be advised to avoid baths and application of any other products to their wound. Patients will be given a diary to record observations about their postoperative wound and to note any adverse events.

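### Infection, a yes/no outcome, is to be compared for non-inferiority with a linear mixed model, which is unsuitable at 24 per arm if infections are few

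*Combined protocol and SAP*

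**What the plan says.** Aim 1 (Objectives) lists the safety endpoints, "including the incidence of wound infection and tolerability using a patient diary". Under Patient Visits and Data Collection, infection is one of the adverse events asked about at every visit, and "Adverse events will be recorded as presence of absence of specific outcomes" [sic]. The Statistical / Data analysis section then puts this outcome and a continuous score into one model: "we intend to model incidence of infection as well as quality of life again across time using linear mixed models". The same sentence makes the safety test one of non-inferiority.

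The documents name no logit link, generalized model, robust variance, or score or exact method. They give no infection rate, non-inferiority margin, alpha or sidedness for this comparison, and do not say whether the deciding contrast is overall or at one visit.

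**The concern.** A linear mixed model assumes normal errors with one residual variance across arms and visits. The variance of a yes/no outcome depends on its risk, and with few events in 24 patients the normal approximation is poor. Two problems follow. The normal-theory upper limit can be too low even when its standard error is right. And where the contrast is at one visit, visits with no infections add zero residuals and pull down the variance used at the visit where infections occur.

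Non-inferiority rests on the upper limit of the laser-minus-sham difference, so a limit that is too low favours declaring the laser safe on a named safety endpoint. With no infections at all, the model has no variance to estimate.

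**Working it through.** **The plan's own figure.** The only sample-size statement is "with alpha = 0.10 and beta = 0.20 suggested 24 participants per group or 48 total were required", for time to epithelialization. No hazard ratio or healing proportion is given, so it cannot be reproduced. If all 48 heal and alpha is two-sided, it implies a hazard ratio of exp(2 × (1.645 + 0.842)/√48) = 2.05. It says nothing about infection.

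**Inputs.** From the documents: 24 v 24 ("patients will be randomized 1:1 to a treatment or control group via computer software"), and four visits ("Immediately after therapy and 4, 8, and 12 weeks postoperative patients will have a follow up visit"), or three if only the follow-up visits enter the model. Assumed: one-sided 5%; margin 10 or 15 points; control risk 2% or 5%; true laser risk = control risk + margin, so that any declaration of non-inferiority is false.

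**Standard error, one outcome per patient.** Correct SE = √[p_L(1−p_L)/24 + p_S(1−p_S)/24]. With equal arms the pooled-variance SE is this times √(24/23) = 1.02, so it is about right. For an effect averaged over visits, the ratio of model SE to correct SE is 1.00-1.04.

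**Standard error, one visit.** If K visits enter and all infections fall at one, the residual variance is averaged over K visits of which K−1 contribute nothing. The SE ratio is then 1/√K: 0.50 for K = 4 and 0.58 for K = 3. Example, 3/24 v 1/24 at week 4:
- Correct SE = √(0.125 × 0.875/24 + 0.0417 × 0.9583/24) = 0.0789.
- A fitted random-intercept model with arm-by-visit terms gives 0.0403 (four visits) or 0.0465 (three).
- Upper limit with the four-visit SE: 0.0833 + 1.645 × 0.0403 = 0.150 (0.1496 before rounding). With the correct SE: 0.0833 + 1.645 × 0.0789 = 0.213.

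The ratio is 0.61-0.71 if infections are mostly at week 4, about 0.87 if they are even over follow-up with an empty first visit, and 1.00 if even over three visits.

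**False non-inferiority.** This is the sum of Binomial(24) × Binomial(24) probabilities over all tables whose upper limit is below the margin:

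| Control risk, margin | Gaussian, one per patient | Plain Wald | Score test | One visit, K = 4 | One visit, K = 3 |
|---|---|---|---|---|---|
| 2%, 10 points | 10.5% | 10.5% | 3.1% | 22.2% | 22.1% |
| 5%, 10 points | 8.7% | 8.7% | 5.0% | 19.8% | 19.2% |
| 2%, 15 points | 7.9% | 7.9% | 3.5% | 27.9% | 21.9% |
| 5%, 15 points | 6.5% | 6.6% | 4.0% | 25.0% | 18.9% |

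Two cautions apply.
- All columns except the score test count 0/24 v 0/24 as a declaration (a zero-width interval). In the first row that table has probability 0.98^24 × 0.88^24 = 0.029, so leaving it out lowers 10.5% to 7.7%. In the last row it is 0.001.
- The one-visit columns use the normal quantile. The two 15-point figures for K = 4 turn on the 3/24 v 1/24 table above, which only just passes. With a t quantile on 46 degrees of freedom they fall to 21.9% and 19.5%.

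**No infections in either arm.** At 2% risk in both arms the probability is 0.98^48 = 0.379. The fitted model returned no standard error. The score upper limit solves δ/√[δ(1−δ)/24] = z, so δ = z²/(24 + z²): 2.706/26.706 = 0.101 (one-sided 5%) or 3.841/27.841 = 0.138 (one-sided 2.5%).

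**The case against.** A reader might infer that the planned analysis halves the standard error and so passes an unsafe laser several times too often. The documents do not support that. Halving needs arm-by-visit terms, a single-visit contrast, every infection at that visit, and four visits in the model, one of them on the day of surgery. The plan says only that the modelling is over time. At visits without infections the pooled SE is too large, so the error does not always run one way.

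A reader might also blame the 6.5-10.5% on the constant-variance assumption. The Wald column shows otherwise: an ordinary interval on two proportions does the same. It is a small-sample failure of normal-theory limits.

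Nor do the documents say that infection is rare, or set a nominal rate for this comparison. The trial is sized on epithelialization, not infection.

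All of this stands and limits the size of the point. It does not rescue the model. Reading the term as shorthand for a generalized linear model is strained, because the same section uses it for temperature. The plan does not exclude the single-visit contrast. The per-protocol analysis could also unbalance the arms: with risks of 5% on sham and 15% on laser, the SE ratio is 0.94 at 24 sham v 18 laser and 0.85 at 24 v 12, though 1.07 at 18 v 24.

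**Conclusion.** The concern holds as a point about unsuitability. A linear mixed model should not decide non-inferiority on a yes/no outcome with 24 per arm if infections are few. In the scenarios worked, false non-inferiority at one-sided 5% is 6.5-10.5% for an overall or one-per-patient contrast, where the standard error is about right. It is about 19-28% for a single-visit contrast with all infections at that visit, which is the extreme case. The score test gives 3-5%. With no infections the linear model gives no usable interval, while the score upper limit is about 10 points (one-sided 5%) or 14 points (one-sided 2.5%). Margin, alpha and infection risk are assumptions throughout. The choice of model and the yes/no recording are in the documents.

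**What to change.** Take infection out of the linear mixed model. Define the endpoint as any infection by week 12, one yes/no per patient. Estimate the laser-minus-sham difference in proportions with a score-type interval (Miettinen-Nurminen or Farrington-Manning) or an exact interval, not a plain Wald interval. Judge non-inferiority by comparing the upper limit with a margin and one-sided alpha stated in advance; without these the comparison cannot be carried out under any model. Any logistic model over visits should carry a small-sample (Firth-type) correction and be supportive only. Keep the linear mixed model for quality of life and temperature.

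The text change is short, but the margin and alpha have to be chosen and justified. The interval will be wider and non-inferiority harder to claim. For example, the 10.1-point score limit with no infections in either arm would not meet a 10-point margin at one-sided 5%.
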